19. To assess the effects of the two diets on methylation patterns in genes of candidate CR pathways;
20. To assess the effects of the two diets on global methylation patterns in PBMCs.

2.a. Primary objectives

Primary objective is to demonstrate that 8-weeks of 5-2 CR plus “healthy living”

counseling in a group of overweight, late middle-aged to aged participants will significantly increase the ratio of plasma exosomal p-panY-IRS-1 to p-S312-IRS-1, compared to baseline and to controls who only receive “healthy living” counseling.

2.b. Secondary objectives

Secondary objectives are noted under specific aims 5-21. Collectively, we aim to demonstrate that 8-weeks of 5-2 CR plus “healthy living” counseling in a group of overweight, late middle-aged to aged participants will significantly improve peripheral insulin sensitivity, decrease fMRI activation in meso-cortico-limbic areas involved in appetitive food salience and reward pathways, increase intrinsic functional connectivity of the DMN, improve brain metabolism, AD biomarker profile and cognitive performance compared to baseline and controls who only receive “healthy living” counseling.

3. Subjects

3.a. Description of study population

The study population will consist of overweight, older (55-70 years old), men and women with evidence of IR and central obesity. The requirement for IR was set because it defines a population at increased risk for AD,⁸⁹ and IR may be responsive to brief³⁹ or extended⁹⁰ CR in overweight human participants. The upper and lower age limits were set because we are interested in the effects of IR and of 5-2 CR on the preclinical phase of AD, at midlife, 15-20 years prior to the onset of clinical disease.

The accrual target is 100 participants to allow for 40 participants that will be successfully enrolled and complete the study and 60 screen failures and withdrawals. Withdrawals will be replaced.

3.b. Inclusion criteria

1. BMI \geq 27; in addition, weight \leq 350 lbs (weight limit for MRI scanner);
2. Age of 55-70 years;
3. HOMA-IR \geq 1.8;
4. MMSE \geq 26

3.c. Exclusion criteria

1. History of cardiovascular disease;
2. History of clinically significant stroke or other neurological disease of the central nervous system;
3. History of substance abuse in the past 6 months or positive urine drug screen;
4. History of clinically significant endocrine disorders (common mild endocrine

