The study is comprised of: an initial telephone pre-screening to describe the study and inclusion/exclusion criteria to potential participants; a "Screening Visit"; randomization into one of two groups; a "Baseline Visit"; the "Outcome Visit" after 8 weeks. During the 8-week period for the 5-2 CR or control groups, participants will return every two weeks for "Compliance Visits", to assess and reinforce dietary compliance in keeping with previous protocols.^{39,40,94} The Outcome Visit will take place at the conclusion of the 8-week phase. Specifically for the 5-2 CR group, the Outcome Visit will be timed during the second of the two CR days. In total, there will be 6 outpatient visits to the NIA Clinical Unit: Screening Visit, Baseline Visit, Week 2 Compliance Visit, Week 4 Compliance Visit, Week 6 Compliance Visit, and the Week 8 Outcome Visit. There will be an additional follow-up phone call or electronic mail within 3 days of completing the Week 8 Visit to assess any problems related to their final visit. Accelerometry will be implemented on two occasions for 96 hours each time: once between the screening and baseline visits and again after the Week 8 Outcome Visit. Throughout the study, additional safety visits may take place for any clinically significant. Participants will be involved in the study for approximately 8 – 11 weeks (allowing for an up to 3 week gap between Screening and Baseline Visits). Study participation will end with completion of accelerometry after the Week 8 Outcome Visit.

It is anticipated that participants in this study will occasionally miss or fail to complete an assessment or procedure, such as a completion of a rating scale or a blood draw. Omissions such as these will be considered expected events and not protocol deviations provided they are infrequent and do not include data needed to assess safety or the primary study outcome. Cumulative proportions of these missed events in the study population will be presented to the IRB annually. In addition, the rate of omissions will be monitored by the Investigators. If an individual misses more than 15% of the required assessments/procedures or if more than 15% of the participants miss completion of the same assessment or procedure, it will be considered a deviation and a deviation report

will be sent to the IRB within two weeks.

Table 1: Procedures

Procedures	Visit 1	Visit 2		Visit 3, 4, 5	Visit 6	
		Week 0		Weeks 2, 4, 6	Week 8	

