This visit will occur within four weeks from the Screening Visit. Participants will arrive on the NIA-Clinical Research Unit after a 12-hour fast. The following procedures will be done: vital signs, anthropometric measurements (weight, waist circumference, sagittal diameter), and a blood draw for clinical labs (CBC, PT, PTT, and INR to ensure safety of the LP), urine pregnancy test (only in women who are able to become pregnant), and research labs including DNA collection (for APOE genotyping and gene expression studies). A 4-hour mixed meal tolerance test will be done. They will also have cognitive testing and will be asked to complete the Symptoms Review Questionnaire, PANAS, and RAND SF-36. A lumbar puncture (LP) will take place; up to a total of 15 mL of CSF will be collected. Participants will have a brain MRI. About 168 mL of blood will be taken during the visit. To facilitate scheduling or satisfy a given participant's request, we may split the various procedures of the Baseline Visit over two days within a week from each other.

4.d.3. 5-2 CR or control groups

At the end of the Baseline Visit, all participants will receive informational materials and one-on-one dietary counseling about "healthy living", consisting of providing and reviewing published material (by the CDC and USDA) on meal portion control, calories in common beverages, meal substitutions for controlling calorie intake, and other dietary considerations. Participants will then be randomized by study investigators into one of two groups to either 1) implement 8 weeks of 5-2 CR (cases); or 2) implement "healthy living" diet (controls).

Participants in the 5-2 group will receive all shakes (Boost®, CWI Medical) from the NIA-Clinical Research Unit.

4.d.4. Compliance visits

To assess and reinforce compliance with their respective diet, we will contact participants by phone or email (via the Secure Email & File Transfer Service: <https://secureemail.nih.gov/bds/Login.do>) at weeks 1, 3, 5, 7 and four days after the Outcome Visit. In addition, we will conduct 2, 4, and 6 week Compliance Visits. The same procedure described below will occur during each one of these.

These visits will take place during the second of the two consecutive restriction days for the 5-2 CR group or any day for the "healthy living" diet group after an 8 hour fast. A blood draw to measure β-hydroxybutyrate, vital signs and anthropometric

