This is a pilot study that is exploratory in nature and one of its goals is to collect preliminary data for multiple outcomes that may be used in future studies on the brain effects of CR.

For the primary and each secondary scalar measure, a separate repeated measures mixed models analysis will be conducted to examine the effects of the between-subjects factor “Group” (5-2 CR group vs. “Healthy living” control group), the within-subjects factor “Time” (Baseline vs. Outcome) and their Interaction. An Auto-Regressive (AR)1 covariance matrix and Restricted Maximum Likelihood Estimation (REML) will be used. We will assess fit to the model using the AIC and BIC criteria (lower values indicate better fit). These parameters were chosen because they are recommended for repeated measures analyses, including fMRI task analyses.¹⁰⁰ Regarding within-subjects effects, we will assess post-hoc differences between the 8-week outcome visit and baseline for the 5-2 CR and control groups and for each group separately (i.e. post-hoc tests for the Group * Time interaction). This analytic approach is common in the CR literature.¹⁰¹ Mixed model post-hoc tests will employ the Least Significant Difference (LSD) statistic. We will use one-tailed t-tests.

Criteria for significance will be set at alpha of 0.05 for all non-MRI analyses, and 0.005 uncorrected at the voxel level for fMRI analyses. Given that this pilot study is exploratory, we will not conduct correction of multiple comparisons for the various secondary outcomes.

Analysis of fMRI data will use a mixed model design to assess the effect of Group on

brain activation associated with viewing appetitive vs. non-appetitive food, the Stroop effect in the Stroop task, and DMN intrinsic functional connectivity. Analyses will be conducted at the whole brain level and within ROIs (vmPFC, OFC and insula for the fMRI food task, lateral and dmPFC for the Stroop task, and in DMN for resting state. The fMRI analyses will be corrected for type 1 error as the cluster level using Monte Carlo simulations.

For brain MRS measures, a repeated measures analysis will be separately used for each of the brain regions of interest: the hippocampus and the prefrontal cortex.

APOE genotype is a common covariate used when assessing populations with AD or at risk for AD. We intend to perform exploratory analyses including APOE, which may reduce error variance and improve our statistical models.

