Plasma ketones are strongly affected by alternate day CR acutely but not chronically;³⁹ our main objective for measuring them is to assess compliance with 5-2 CR.

We do not anticipate a change in physical activity in 5-2 CR versus “healthy living” control groups, because no change has been noted in our previous studies. Nonetheless, this is a common analysis requested by reviewers, to make sure that exercise effects did not contaminate diet effects.

The data from the gene array and DNA methylation array will be analyzed using residuals after adjustment for white blood cell differential count in linear regression models. We will take two approaches to analyze the data. First we will focus on candidate genes approach where we select specific expression probe or CpG sites; DNA for these studies will be collected during Baseline, Compliance and Outcome Visits. Second, we will run genome-wide association analysis for differences in cross sectional and longitudinal changes in gene expression or DNA methylation between the control and 5-2 CR group at each gene array probe or CpG site. DNA for genome-wide association analyses will only be collected during Baseline and Outcome Visits. For the cross sectional analyses, we will use a paired t-test at each visit, and mixed models for longitudinal analysis. In addition, we will look at overall patterns of gene expression and methylation using principle components, DIANE and hierarchical clustering tools to determine whether there are specific gene expression and methylation signature in association with 5-2 CR. As secondary analyses, we will also determine whether gene expression and DNA methylation patterns can predict the changes in metabolic, cognitive and neurochemical variables collected in this study. Within the 5-2 CR group, we will test the association between baseline levels of gene expression or DNA methylations at each probe/CpG site with longitudinal changes in the main outcome variables using mixed models.

10. b. Power analysis

The accrual number request is 100 participants. Our target sample size for completing the study is $N = 40$. There will be 20 participants in each group. We anticipate up to 60 participants will not meet inclusion criteria during the screening visit or may withdraw from the study. Enrollment will continue and withdrawals will be replaced until we have acquired complete data from 40 participants.

For power calculations, we used G*Power (<http://www.gpower.hhu.de/en.html>).

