Regarding our primary outcome (exosomal p-Ser312-IRS-1/p-panY-IRS-1), in our published study, we examined differences between preclinical samples from participants who eventually developed AD (92.1 ± 7.7) and controls (14.7 ± 0.9)⁵¹. We base our power analysis on the assumptions that the our subjects at high risk for AD had intermediate high values for p-Ser312-IRS-1/p-panY-IRS-1 ratio at baseline (ratio = 46), that the 5-2 CR intervention had a similar modest effect size as for peripheral IR in decreasing the ratio (0.3), whereas the control intervention induced no change. We used the following input parameters to determine power for ANOVA repeated measures, between-within interactions: $\alpha = .05$ (one tailed); 2 groups (5-2 CR vs. Healthy Living diet); 2 repeated measures (Baseline vs. Outcome); correlation between repeated measures = 0.4. Based on these parameters, we achieve over 90% power with a total 40 participants (see Figure 4 below for post-hoc power calculation (achieved power, given certain N and effect size)). These calculations are conservative (e.g. the effect size may be greater than 0.3); therefore, it is likely that we will actually achieve greater power in this study.

[figure not shown]

Figure 4. Post-hoc power calculation for primary outcome (exosomal p-Ser312-IRS-1/p-panY-IRS-1) analyzed with ANOVA for repeated-measures for within-between interaction. The x-axis depicts total sample size and the y-axis depicts Power.

In addition, we performed power calculations for several key secondary outcomes of interest.

Regarding fMRI, we performed power calculations based on a series of equations by Mumford and Nichols¹⁰⁰ that take into account the unique nature of fMRI data. We use an alpha = .005 for fMRI analyses, as recommended by Mumford and Nichols.

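### The Group x Time test is a change-score comparison; at the plan's own correlation of 0.4, adjusting week 8 for baseline would cut the variance of the diet effect by about 28%

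*Combined protocol and SAP*

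**What the plan says.** Section 10.a sets one model for all scalar outcomes: "For the primary and each secondary scalar measure, a separate repeated measures mixed models analysis will be conducted to examine the effects of" the between-subject factor Group, the within-subject factor Time and their interaction ("Baseline vs. Outcome) and their Interaction"). It uses an AR(1) covariance, REML and one-tailed tests at 0.05. Each group has its own baseline mean. The only covariate named for these outcomes is APOE genotype, in exploratory analyses.

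Section 10.b powers the primary outcome, the exosomal IRS-1 ratio, as a between-within interaction with f = 0.3 and "correlation between repeated measures = 0.4". It plans 20 per group and says that "withdrawals will be replaced until we have acquired complete data from 40 participants". It reports power above 90%.

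Three other places bear on the point:

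- Section 10.a describes the trial as an exploratory pilot and says that "one of its goals is to collect preliminary data for multiple outcomes that may be used in future studies".
- The primary objective (section 2.a) is a change compared to "baseline and to controls who only receive" counselling, so it covers a within-group and a between-group comparison.
- Section 4.d.1 lists "randomization into one of two groups" before the Baseline Visit. Section 4.d.3 places it after the end-of-visit counselling: "Participants will then be randomized by study investigators into one of two groups to either" start 5-2 CR or follow the control diet.

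**The concern.** A change score subtracts the whole baseline value, as if each unit at baseline predicted a full unit at week 8. At a correlation of 0.4 with equal variances, it predicts only 0.4 of a unit. Subtracting all of it adds noise, so the planned contrast is less precise than a week-8 comparison that ignores baseline altogether. Baseline adjustment estimates the slope from the data and removes only the part that predicts.

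Neither bias nor validity is in question; precision is. A pilot meant to inform later studies delivers estimates, and their usefulness depends on their interval width. The planned effect is also uncertain: section 10.b carries f = 0.3 over to the exosomal ratio from peripheral insulin sensitivity, relying partly on a 12-month restriction study, for an 8-week diet. Each completer undergoes two lumbar punctures, two MRI sessions and two 4-hour meal tests, so lost precision is expensive to recover by recruiting.

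**Working it through.** **Inputs.** From section 10.b: correlation ρ = 0.4, f = 0.3, n = 20 per group (N = 40), 2 visits. From section 10.a: α = 0.05, one-tailed. Variance is taken as equal at both visits, as the AR(1) structure implies. Effects are in units of the outcome's SD.

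**1. The plan's own power.** For the between-within interaction, λ = f² × N × 2 / (1 − ρ) = 0.09 × 40 × 2 / 0.6 = 12. The noncentral F with 1 and 38 df gives 0.92 at α = 0.05, and 0.96 for the one-tailed test. Both agree with the stated figure of over 90%. The implied group difference in change follows from √12 × √(1.20 × 2/20) = 3.464 × 0.346 = 1.2 SD.

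**2. Equivalence.** In a simulated complete data set of 40 participants, the REML Group x Time term was −0.0596 (SE 0.3581). The difference in mean change was the same: −0.0596 (SE 0.3581).

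**3. Variance factors** (each multiplied by 2σ²/n):

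| Contrast | Formula | ρ = 0.4 |
|---|---|---|
| Change score (planned) | 2(1 − ρ) | 1.20 |
| Week 8 only | 1 | 1.00 |
| Baseline-adjusted, large sample | 1 − ρ² | 0.84 |
| Baseline-adjusted, N = 40 | (1 − ρ²) × 37/36 | 0.863 |

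The factor 37/36 = 1 + 1/(N − 4) is the price of estimating the slope. The ratio is 0.863/1.20 = 0.719, a cut of 28% (30% in large samples). The equivalent sample size is 40/0.719 = 55.6.

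**4. Precision and power.** The standard errors are √(1.20/10) = 0.346 SD and √(0.863/10) = 0.294 SD.

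| Quantity | Planned (38 df) | Adjusted (37 df) |
|---|---|---|
| 95% interval half-width, SD | 0.70 | 0.60 |
| One-tailed power at 1.2 SD (plan) | 0.961 | 0.991 |
| One-tailed power at 0.8 SD (assumed) | 0.733 | 0.848 |
| Effect detectable with 80% power, SD | 0.88 | 0.74 |

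A simulation of 40,000 trials agreed: variance ratio 0.72; power 0.961 and 0.991 at 1.2 SD, 0.731 and 0.848 at 0.8 SD; type I error 0.052 for both methods.

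**5. Other correlations.** The ratio is (1 + ρ)/2 × 37/36. Section 10.b gives no correlation for the secondary outcomes, so the range below is assumed.

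| ρ | Ratio | Change in variance |
|---|---|---|
| 0.2 | 0.617 | −38% |
| 0.4 | 0.719 | −28% |
| 0.7 | 0.874 | −13% |
| 0.9 | 0.976 | −2% |
| 0.95 | 1.002 | +0.2% |

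Break-even is at ρ = 35/37 = 0.946.

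**6. Unequal variances.** Let k be the ratio of the week-8 SD to the baseline SD. The ratio becomes k²(1 − ρ²) × (37/36) / (1 + k² − 2ρk). At ρ = 0.4 it is 0.50 for k = 0.75, 0.72 for k = 1, 0.86 for k = 1.25 and 1.02 for k = 2. At ρ = 0.7 and k = 1.25 it is 1.01. The loss cannot exceed the slope-estimation factor of 37/36, or 2.8%.

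**The case against.** The planned contrast is an accepted method, matches its power calculation and exceeds 90% power. At the planned effect, adjustment moves power only from 0.96 to 0.99. The 0.8 SD example is not in the documents and lies near the peak of the power gain: about 0.12 near 0.7 SD, but only 0.07 at 0.4 SD and 0.02 at 0.2 SD. All of this is true, and it makes the point one of efficiency rather than error. The 28% variance cut, however, does not depend on the size of the effect.

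The 28% does depend on equal variances and on an unsourced correlation. That stands as a condition. Both are the plan's own working assumptions, and departures cost at most 2.8% while the gain can exceed 28%.

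Plain ANCOVA drops a participant who lacks either visit, and section 4.d.1 expects some missed assessments for outcomes other than the primary. ANCOVA also gives no within-group change, which section 2.a asks for. Both objections have force against plain ANCOVA. Neither applies to the mixed model with a shared baseline mean, which keeps partial records and estimates both contrasts in one fit.

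Finally, baseline precedes the diet whichever randomisation text is followed, because section 4.a.1 supplies the shakes only at the end of the Baseline Visit. That is correct, but it does not show that baseline was measured before allocation was known.

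**Conclusion.** The point holds. The planned Group x Time test is a change-score comparison. At ρ = 0.4 with 20 per group, it has 1.20/0.863 = 1.39 times the variance of the baseline-adjusted comparison. This is lost precision in a valid analysis, worth correcting because the trial is small, its estimates are meant to guide later work and the remedy is nearly free. The size rests on the plan's correlation, equal variances at the two visits, a common baseline slope and complete pairs. For the secondary outcomes the direction is the same across most plausible correlations, but the documents do not allow the size to be fixed.

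**What to change.** 1. **Section 10.a.** Make the primary estimate the week-8 group difference adjusted for the baseline value of the outcome (ANCOVA). Alternatively, keep the REML mixed model and give both groups one baseline mean. Fit that version to all randomised participants: randomisation justifies equal baseline means among them, but not necessarily in a set of completers with replacements.
2. **Secondary scalar outcomes.** Use the same form. The shared-baseline model is preferable where visits are missing.
3. **Section 10.b.** Name the same model in the power analysis.
4. **Interpretation.** Read the diet effect from the between-group contrast. Continue to report the change from baseline that section 2.a declares, but do not treat it alone as evidence of a diet effect.
5. **Sections 4.d.1 and 4.d.3.** Reconcile when randomisation takes place, so that the baseline value is clearly measured before it.

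The cost is wording, one degree of freedom and one clarification. No new data or procedures are needed. With equal variances, an outcome correlated above 0.946 between visits would lose a negligible amount (0.2% more variance at 0.95).
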